14.3 SAFETY DATA

Adverse events

Table	Title	Pop	Top.Line
14.3.1.1	Summary of Treatment Emergent Adverse Events (TEAEs)	SAF	X
14.3.1.2.1	Treatment Emergent Adverse Events by System Organ Class and Preferred Term	SAF	
14.3.1.2.2	Treatment Emergent Ocular Adverse Events by System Organ Class and Preferred Term	SAF	
14.3.1.3	TEAEs by SOC and PT by worst severity	SAF	
14.3.1.4	TEAEs by SOC and PT by worst relationship	SAF	
14.3.1.5	TEAEs related to IMP/Placebo	SAF	
14.3.1.6	TEAEs leading to discontinuation	SAF	
14.3.1.7	Serious TEAEs	SAF	
14.3.1.8	Serious TEAEs related to IMP/Placebo	SAF	
14.3.1.9	TEAEs AESI	SAF	
14.3.1.10	TEAEs AESI related to IMP/Placebo	SAF	
14.3.2	Listings of Deaths Other Serious Adverse Events, and OtherSignificant Adverse Events	SAF	

14.3.3 [This title is reserved for narratives.]

Study Code: CLOBOF3-16IA01 Date: 09-JUL-2021

NCT No.: NCT04246801

Sponsor: Laboratorios Salvat, S.A.

Other Safety assessments

Table	Title	Pop	Top.Line
14.3.4.1	Absolute and Percentage change from Baseline in Vital Signs by treatment regimen. Descriptive Statistics	SAF	
14.3.4.2	Summary statistics. Change from Baseline to Day 3, Day 8, Day 15 and Day 29 compared to placebo in intraocular pressure (IOP).	SAF	X

Treatment exposure

Table	Title	Pop	Top.Line
14.3.5.1	Compliance with IMP/Placebo % (doses/amount). Descriptive statistics.	SAF	
14.3.5.2	Exposure to IMP/Placebo: Duration of treatment Number ofdoses completed/not completed, and reasons by treatment regimen. Descriptive statistics	SAF	

Concomitant medications

Table	Title	Pop	Top.Line
14.3.10.1	Summary of Prior Medications and Therapies tabulated by ATC level 3 group and generic medication name	SAF	
14.3.10.2	Summary of All Concomitant Medications (rescue and prohibited medications included) and Therapies tabulated by ATC level 3 group and generic medication name	SAF	
14.3.10.3	Summary of Concomitant Medications (Rescue and prohibited) tabulated by ATC level 3 group and generic medication name	SAF	

Sponsor: Laboratorios Salvat, S.A. Study Code: CLOBOF3-16IA01 NCT No.: NCT04246801

8.2 Listings of individual patient data and other information to be produced for the clinical study report (sections 16.1 and 16.2 according to ICH E3)

Listing	Title	Pop	Top.Line
16.1.7	Randomisation scheme	ALL	

Patient disposition

Listing	Title	Pop	Top.Line
16.2.1.1	Patient Disposition	ALL	
16.2.1.2	Screening Failures, Discontinued Subjects, Reason for Discontinuation	ALL	X
16.2.1.3	Visits dates		
16.2.2.1	Protocol Deviations	ALL	
16.2.3.1	Patients excluded from SAF	ALL	
16.2.3.2	Patients excluded from FAS	ALL	
16.2.3.3	Patients excluded from PP	ALL	

Demographic and baseline characteristics

Listing	Title	Pop	Top.Line
16.2.4.1	Demographic data	SAF	
16.2.4.2	Relevant Medical History	SAF	
16.2.4.4	Urine Pregnancy test	SAF	
16.2.4.5	Cataract diagnosis	SAF	
16.2.4.5	Inclusion Criteria Not Met and Exclusion Criteria Met	SAF	

Compliance

Listing	Title	Pop	Top.Line
16.2.5	Compliance with IMP/Placebo	SAF	

Efficacy data

Listing	Title	Pop	Top.Line
16.2.6.1	Slit Slamp Examination	SAF	
16.2.6.2	BCVA by Snellen chart	SAF	
16.2.6.3	Eye pain (VAS)	SAF	
16.2.6.4	Eye discomfort	SAF	
16.2.6.5	Photophobia	SAF	

Sponsor: Laboratorios Salvat, S.A. Study Code: CLOBOF3-16IA01

NCT No.: NCT04246801

16.2.6.6	Indirect ophthalmoscopy	SAF	
----------	-------------------------	-----	--

Adverse Events

Listing	Title	Pop	Top.Line
16.2.7.1	Adverse Events	SAF	

Other Safety assessments

Listing	Title	Pop	Top.Line
16.2.9	Vital signs	SAF	
16.2.10.1	Physical examination	SAF	
16.2.10.2	Eye examination	SAF	
16.2.11	IOP measurementsby Goldman Tonometer	SAF	

Concomitant medication

Listing	Title	Pop	Top.Line
16.2.12.1	Prior Medications and Therapies tabulated by ATC level 3 group and WHO preferred name	SAF	
16.2.12.2	All Concomitant Medications and Therapies tabulated by ATC level 3 group and WHO preferred name	SAF	
16.2.12.3	Rescue and prohibited Concomitant Medications tabulated by ATC level 3 group and WHO preferred name	SAF

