2.3 Risk-Benefit Assessment

Benefits

Clobetasol is a synthetic fluorinated corticosteroid. The corticosteroids constitute a class of primarily synthetic steroids used topically as anti-inflammatory and antipruritic agents. Older corticosteroids have been used since the 1950's, while new molecules were more recently developed and have been proven effective in controlled clinical trials.

Ophthalmic corticosteroids have a very well-known effect by decreasing the number and function of inflammatory cells, vascular permeability, and by inhibiting chemical mediators of inflammation, thus it could be considered that corticosteroids have a class effect for their indications in post-surgical inflammation.

Particularly, clobetasol propionate has been approved for the treatment of other inflammatory topical processes for over 30 years (Temovate® Cream) showing a positive benefit-risk profile as its efficacy is widely demonstrated with a good safety profile. Moreover, the use of corticosteroids for short-term treatment of local inflammation, usually in the anterior segment of the eye (including inflammation post-surgery) is widely supported in the literature.

Risks

It is known that exogenous corticosteroids can cause hypertension and other cardiovascular adverse effects including a hypercoagulability state and dyslipidemia. However, these adverse effects are linked to long-term systemic exposure to corticosteroids.

Ocular administration of clobetasol propionate and other corticosteroids have been linked to rare ocular adverse events (AEs) such as IOP elevation, cataracts, ocular hypertension, glaucoma or inhibition of wound healing. The limited exposure planned for this study (one drop QID/14 days) aims to prevent these rare AEs.

Benefit-Risk Assessment

Topical corticosteroids are safer than systemic glucocorticoids due to the lower systemic exposure. Furthermore, ocular administration results in even lower systemic exposure, below

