6.7.1 Prohibited Concomitant Medications

The use of the following medications is not permitted during the study:

- Any systemic or local therapy with corticosteroids (other than the study drug) or immunosuppressant (except pre-surgical and/or surgical administration of 1 drop of a topical NSAID or corticosteroid, at the investigator discretion)
- Any topical ocular medication (except preservative-free antibiotics for prophylactic purposes and preservative-free artificial tears).
- Any systemic NSAID or opioids drugs (except occasional use of OTC formulations titrated no more than one single dose per week)

The aforementioned medications will be considered as rescue medications when administered in patients not responding to the IMP (Section 6.7.2).

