6.7.2 Rescue Medication

Any patients not responding adequately to the IMP may be rescued and placed on alternate therapy (Section 6.7) at the investigator's discretion at any time.

The choice of rescue medication is at the investigator's discretion. Any patient placed on rescue therapy will discontinue the use of the IMP and the investigator must made extensive efforts to ensure that the patient will attend all his/her remaining study visits until study completion, aiming to collect the most complete efficacy and safety data.

Additionally, patients will be asked to phone the study center at any time to speak to a member of the medical personnel should they experience any worsening of ocular conditions or other AFs

Rescued patients will be considered treatment failures, but the need for rescue therapy will not be considered an AE.

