8.3.10 Precautions/Overdose

The risk of overdosing in general in this study is considered to be very low. The planned maximum exposure will be approximately 0.066 mg/day of clobetasol propionate (approximately 0.924 mg of clobetasol propionate over a period of 14 days). The total amount of clobetasol propionate administered in the toxicological pre-clinical study (at the highest dose) was 4 times above the clinical trial dose, exhibiting no ocular toxicity. Systemic HED in pre-clinical study was 17-times higher compared to dosing in one eye of adults.

An expected AR that could represent a severe condition is the induction of IOP rise (and associated ocular pain and redness). In case of IOP >30mmHg, the investigator discretion is advised, using preferred standard of care at the study site. The use of specific ocular hypotensor eye drops (like beta blockers / alpha agonists / carbonic anhydrase inhibitors) is recommended.

Nevertheless, unintentional administration of any dose that deviates from the scheduled regimen will be documented and reported by center personnel.

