5 DATA SETS TO BE ANALYSED

The following analysis sets will be used for the statistical analysis and presentation of data:

• Full Analysis Set (FAS): The FAS will be the primary analysis set for the efficacy endpoints and will include all randomized patients. The FAS population will be analyzed according to the planned treatment (rather than treatment actually received).

Statistical Analysis Plan Sponsor: Laboratorios Salvat. S.A. Version: Final 3 Study Code: CLOBOF3-16IA01 Date: 09-JUL-2021

NCT No.: NCT04246801

Full Analysis Set without including rescued subjects (FAS non-RM set): The FAS non-RM will be the analysis set for the efficacy endpoints and will include all randomized patients without including rescued subjects (prohibited medication allowed.

- Safety Analysis (SAF) set The safety set will be the primary analysis set for the safety endpoints and will include all randomized patients who instilled at least one dose of IMP or placebo. The SAF will be analyzed according to the treatment actually received.
- Per Protocol (PP) Population: The PP population set will be tested to confirm the robustness of the efficacy analyses and will include all patients in the FAS who have no major protocol deviations (i.e. patients who comply the protocol sufficiently to ensure that the data exhibits the effects of the IMP or placebo when administered as intended). Protocol violations include: violations of entry criteria, lack of compliance and the use of prohibited medication. The PP population will be analyzed according to the treatment actually received.

Lack of compliance is defined as less than 80% compliance (section 6.3.8).

Efficacy analyses will be based on both the FAS and the PP, but the FAS will be considered the primary analysis population.

Safety analyses will be based on the SAF.

Primary efficacy and key secondary efficacy analysis will be performed for all efficacy endpoints, analyzing:

-all subjects who were randomized (i.e., FAS set),

AND

-all subjects who were randomized without including rescued subjects (i.e., FAS non-RM set)

Secondary efficacy analysis will be performed analyzing all subjects included in the FAS non-RM populations, hereinbefore described.

Sensitivity analysis described in the section 6.3.7 will be performed analyzing all subjects included in FAS set populations, hereinbefore described.

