6.3.2 Summary Statistics

Data will be summarised by means of summary statistics. For continuous data the following summary statistics will be presented: number of observations, mean, standard deviation (SD), minimum, Q1, median, Q3 and maximum. 95% CI of the mean will also be presented for efficacy and safety data. Change from baseline to each post-baseline visit will be also described using descriptive statistics. Categorical data will be presented as counts and percentages.

Summary statistics will be presented by treatment group and visit, as applicable.

Certain presentations (withdrawals, patient exclusion from datasets, baseline and background characteristics and primary efficacy data) may be broken down by study center, if relevant.

All data collected during study follow-up will be displayed and analyzed according to the actual visit data in the eCRF.

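### Table 14.3.4.2, the only by-arm table of measured IOP, pools readings taken after rescue corticosteroid and after IOP-lowering drops, so the mean difference can be diluted, and no on-treatment view is planned beside it.

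*SAP*

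**What the plan says.** **The IOP output.** SAP section 14.3 lists Table 14.3.4.2, "Summary statistics. Change from Baseline to Day 3, Day 8, Day 15 and Day 29 compared to placebo in intraocular pressure (IOP"), on the safety set (SAF) and marked as top-line. Otherwise measured IOP appears only in patient listing 16.2.11. SAP 6.3.11, on other safety assessments, does not describe IOP.

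**Who and which readings.** The SAF "will include all randomized patients who instilled at least one dose of IMP or placebo" (SAP 5). SAP 6.3.2 adds: "All data collected during study follow-up will be displayed and analyzed according to the actual visit data in the eCRF". No rule drops, flags or shows separately the readings that follow rescue or IOP-lowering treatment.

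**Rescue.** Protocol 6.7.1 lists prohibited drugs, including systemic and local corticosteroids, and states: "The aforementioned medications will be considered as rescue medications when administered in patients not responding to the IMP". Under 6.7.2, "Any patient placed on rescue therapy will discontinue the use of the IMP", and sites must try to have the patient "attend all his/her remaining study visits until study completion". Protocol Table 1 schedules IOP at every visit. The rescue drug is the investigator's choice.

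**IOP as a named risk.** Protocol 2.3 says that ocular administration of "clobetasol propionate and other corticosteroids have been linked to rare ocular adverse events (AEs) such as IOP elevation". Protocol 8.3.10 calls an IOP rise an expected reaction and, in the paragraph on IOP above 30 mmHg, says: "The use of specific ocular hypotensor eye drops (like beta blockers / alpha agonists / carbonic anhydrase inhibitors) is recommended".

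**What exists elsewhere.** An IOP rise over 30 mmHg is an adverse event of special interest, tabulated in 14.3.1.9 and 14.3.1.10. Treatment-emergent events run from first to last dose (SAP 6.3.1). SAP 5 defines a set without rescued patients (FAS non-RM), for efficacy only.

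**The concern.** A placebo patient rescued with a corticosteroid between Visits 2 and 3 stays in the placebo column and contributes steroid-exposed IOP at Visits 3, 4 and 5. A patient on active treatment whose IOP rises and who is given hypotensive drops contributes lowered readings from then on. If the first happens more on placebo and the second more on active, both pull the mean difference toward zero. For a safety measure that is the unsafe direction.

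This matters here because Protocol 2.1.4 reports no earlier clinical trial of the product in the proposed indications, and because the protocol itself names IOP elevation as a corticosteroid risk. The SAP is also uneven. It closes the adverse event window at the last dose and builds a rescue-free set for efficacy, yet it gives measured IOP only an all-readings view.

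**Working it through.** The plan states no IOP effect, rescue rate, steroid share of rescue or use of IOP-lowering drops. It therefore has no figure of its own to reproduce on this point, and every input below is an assumption.

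**1. Model.** Let
- d = IOP effect of clobetasol (mmHg), and dr = IOP effect of the rescue steroid;
- rp, rc = proportion rescued on placebo and on clobetasol;
- s = share of rescue that is a corticosteroid;
- w = share of d still present at the visit;
- h = net share of the clobetasol arm on IOP-lowering drops, and L = mmHg lowered.

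Rescued patients stop study drug, so the observed difference in mean change is

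D = w·d·(1 − rc) + dr·s·rc − dr·s·rp − h·L = w·d·(1 − rc) − dr·s·(rp − rc) − h·L.

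**2. On treatment, before drops.** With w = 1, dr = d and h = 0, D/d = (1 − rc) − s·(rp − rc).

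| rp / rc | s = 0.5 | s = 1 |
|---|---|---|
| 10% / 5% | 0.95 − 0.025 = 92.5% | 0.95 − 0.05 = 90% |
| 25% / 10% | 0.90 − 0.075 = 82.5% | 0.90 − 0.15 = 75% |
| 40% / 15% | 0.85 − 0.125 = 72.5% | 0.85 − 0.25 = 60% |

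With s = 1 the expression reduces to 1 − rp, which agrees with the last column.

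**3. Adding drops.** With L = 8 mmHg, h = 2% removes 0.02 × 8 = 0.16 mmHg and h = 5% removes 0.05 × 8 = 0.40 mmHg. Over d = 1 to 3 mmHg, the smallest result is at d = 1 with 40/15% rescue, all steroid: 0.60 − 0.40 = +0.20 mmHg. In this range the on-treatment difference shrinks but does not change sign.

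**4. Day 29.** Dosing lasts 14 days, so Day 29 is about two weeks after the last planned dose. Without drops, D is negative only if w < s·(rp − rc)/(1 − rc):
- 10/5%: 2.6% (s = 0.5) to 5.3% (s = 1)
- 25/10%: 8.3% to 16.7%
- 40/15%: 14.7% to 29.4%

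With w = 0 and d = 2 mmHg, D runs from −2 × 0.025 = −0.05 to −2 × 0.25 = −0.50 mmHg. A negative value needs the clobetasol effect largely gone while rescue steroid still acts.

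**5. Would censoring by visit recover the lost elevation?** Suppose 5% of the active arm (7 of 140) sits 14 mmHg above the rest, whose mean is a.
- Without drops the mean is a + 0.05 × 14 = a + 0.7.
- After drops bring the seven back to the others, it is a.
- After censoring the seven, the remaining 133 also average a.

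A by-visit mean censored at drops therefore repeats the lowered value. Only a summary that keeps each patient's highest reading before drops retains the seven elevations.

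**The case against.** The case against is substantial.

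- **Large rises are already counted.** The special-interest tables cover IOP above 30 mmHg by arm. Their window ends at the last dose, so a placebo rise that starts after a switch to rescue steroid is left out, while a rise that later prompts drops counts from its onset. For large rises this is close to an on-treatment view.
- **The confounders are visible.** Table 14.3.10.3 summarises rescue and prohibited medication. Under SAP 6.3.9 most ocular-route drugs count as prohibited if they are not rescue. Patient listings give detail, and by-visit summaries include the upper quartile and maximum.
- **No inference is at stake.** SAP 6.3.10 limits safety comparisons to description. Showing all observed readings on the safety set is a legitimate choice, and a set defined by post-randomization rescue is no model for safety.
- **Direction and size are assumed.** The planning rates of 0.22 and 0.07 for clearing imply 78% and 93% not cleared, but not clearing is not the same as being rescued. Entry criteria also remove eyes with glaucoma, ocular hypertension or IOP of 24 mmHg or more, and patients with a previous steroid response.

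Most of this stands, and it limits the point to a missing supplementary display. It does not remove the point. The event tables do not summarise smaller rises as measurements. They can also miss a rise dated to Visit 4 (Day 15 ± 2 days) if dosing has already stopped. The medication tables are not linked to IOP readings, and nothing corrects the means in the top-line table.

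**Conclusion.** The point holds as a gap in presentation. The one by-arm table of measured IOP mixes readings under assigned treatment with readings under rescue steroid or IOP-lowering drops, and nothing shows the first kind alone. Dilution follows if placebo patients receive more rescue corticosteroid or if drops are used mainly on active. Under the assumed rates and dr = d, 60% to 92.5% of the on-treatment effect remains, less a further 0.16 or 0.40 mmHg for drops. The true size cannot be derived from the documents.

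A reader might infer three stronger things that the documents do not support:

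- That Table 14.3.4.2 is the only by-arm IOP output. It is the only one of measured values.
- That the effect is certainly diluted, and in proportion to placebo failure. No rescue rate or steroid share is given, and the choice of rescue drug is open.
- That a reversed sign at Day 29 would be dilution of the treatment effect. It would mix washout with continuing rescue and should not be described that way.

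**What to change.** Keep Table 14.3.4.2 unchanged. Add one descriptive SAF table by arm, using only readings up to the last dose of study medication and before the first rescue corticosteroid or first IOP-lowering medication, and showing:

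- each patient's maximum IOP and maximum change from baseline;
- the last such reading, including early-termination readings, and unscheduled readings where recorded (Protocol 4.3.2.7 does not require IOP there);
- the proportion above the protocol's own 30 mmHg threshold;
- by visit, the change from baseline, with the number censored per arm and the reason.

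State how a reading taken shortly after the last dose is assigned. Visit 4 follows 14 days of dosing, so a strict cut could lose most end-of-treatment readings, and early-termination readings could be lost in the same way.

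Label the table supportive. Censoring is informative: it removes patients with high IOP from later visits, and rescued eyes as well. The maximum-value rows carry the information that by-visit means lose.

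The cost is a short SAP paragraph and one table from data already planned for collection (IOP, dosing dates, medication start dates and the rescue flag). The drawback is fewer patients at later visits. No dose, visit or clinical rule changes.

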6.3 Hypotheses and Statistical Methods

6.3.1 Definitions

Baseline	(Visit 1 (Day 1, 24 h after the cataract surgery).				
Time calculation	Differences between dates to express duration will be calculated as the final date - initial date + 1. To convert these days differences to other units, the following conversion factors will be used: 1 year = 365.25 days and 1 month = 30.4375 days.				
	Ex. Age = (informed consent date – date of birth + 1) / 365.25				
Absolute change	Absolute change from Baseline at Visit X will be calculated as:				
from Baseline	Absolute change from Baseline = Visit X - Baseline				
Percentage change	Percentage change from Baseline at Visit X will be calculated as:				
from Baseline	Percentage change from Baseline [%] = ((Visit X - Baseline)/Baseline) *100				
	In case of Baseline = 0 no percentage change from baseline will be calculated.				
Signs of ocular inflammation (yes/no)	The presence/absence of the different signs of ocular inflammation: Chemosis, Bulbar conjunctival injection, ciliary injection, corneal edema, keratic precipitates will be defined as:				
	No: grade=0 (absence)				
	Yes: grade=1, 2 or 3 (presence)				
Conversion Snellen	Step 1. Mar = Snellen Denominator/Snellen Numerator				
to LogMar	Step 2. LogMar = log (Mar)				
	Example: Snellen 20/40				
	Mar = 40/20 = 2				
	LogMar= log(2) = 0.3				
Treatment Emergent Adverse Event	Treatment Emergent Adverse Events (TEAEs) are defined as an event that emerges during treatment having been absent pretreatment or worsens relative to the pre-treatment state:				
	First dose IMP/Pacebo date ≤ start date AE ≤ last dose IMP/Placebo date				
Rescue medication	The following prohibited medications will be considered as rescue medication when administered to subjects not responding to IMP or placebo:				
	 Any systemic or local therapy with corticosteroids (other than the study drug) or immunosuppressant (except pre- surgical and/or surgical administration of 1 drop of a topical NSAID or corticosteroid, at the investigator discretion) 				

Date: 09-JUL-2021

Sponsor: Laboratorios Salvat, S.A. Study Code: CLOBOF3-16IA01

NCT No.: NCT04246801

	 Any topical ocular medication (except preservative-free antibiotics for prophylactic purposes and preservative-free artificial tears) Any systemic NSAID or opioids drugs (except occasional use of OTC formulations titrated no more than one single dose per week) 			

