6.3.8 Exposure to Treatment

Subjects will record each IMP or placebo administration (e.g., one drop every six hours, during 14 days) on their dispensed diaries.

Compliance is defined as the percentage of actual doses the patient instilled with respect to the number of total doses planned. The planned dose is always one drop of IMP or placebo. Compliance will be summarized categorically (<80%, ≥80% and 100%) by treatment regime. It will be calculated as follows:

Compliance of IMP/Placebo administered %= (num. of doses instilled / num. of planned doses))(ml))*100

Planned doses=56

Compliance at last visit with IMP/Placebo is defined as the percentage of actual doses the patient instilled with respect to the number of total doses planned at the time of the last visit with IMP/Placebo.

Compliance of IMP/Placebo administered % at last visit with IMP/Placebo = (num. of doses instilled / num. of planned doses at last visit with IMP/Placebo))(ml))*100

Date: 09-JUL-2021 NCT No.: NCT04246801

Planned doses at last visit with IMP/Placebo = (End date IMP/Placebo exposure – First date IMP/Placebo exposure+1)*4.

Sponsor: Laboratorios Salvat, S.A.

Study Code: CLOBOF3-16IA01

Compliance at visit 3 (day 8±1) is defined as the percentage of actual doses the patient instilled with respect to the number of total doses planned at visit 3.

Compliance of IMP/Placebo administered % at visit 3= (num. of doses instilled / num. of planned doses at visit 3) (ml))*100

Planned doses at visit 3=32

In case a scheduled dose was not administered (missed) the missed dose and the reason will be captured in the eCRF as per the patient diary and tabulated by treatment regimen.

All compliance data will be summarized and listed for the SAF.

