6.3.9 Concomitant Medications

All concomitant medications/therapies will be classified according to ATC level 3 group text and generic medication name. The medications will be divided into two categories based on start date and end date: Prior Medications and Concomitant Medications: .

- Prior Medications: start date and end date before first day of IMP
- Concomitant Medications:
 - Start date before first day of IMP and end date after or on same day as first day of IMP or no end date, i.e. ongoing after first day of IMP; or
 - Start date after or on same day as first day of IMP

Within concomitant medications, a distinction will be made between rescue medication and prohibited medication.

Incomplete dates will be handled as follows:

- If the start and stop date for a concomitant medication are completely missing, it will be assumed that the medication was started before treatment and classified as Prior Medication.
- If only the start date is missing the medication will be classified as:
 - o Prior if end date is before first day of IMP
 - Concomitant if end date is on or after first day of IMP
- If only the end date is missing the medication will be classified as
 - Concomitant if start date is before or on same day as Day 15
- If the year and/or month are available, medication start in relation to the first day of IMP will be evaluated as close as possible (e.g., if only the year when the medication was started is available and ongoing is checked, the medication will be classified as a Concomitant Medication).
- If the medication was started in the same month as the first day of IMP, the medication will be classified as a Concomitant Medication.

Relative day will generally be calculated for all medications except for the ones with an incomplete start date.

Data will be listed for the SAF. Subject's medications will be presented separately for each timing (i.e. prior, and concomitant medications) in 2 summary tables. In addition, a summary table for rescue and prohibited medication will be presented distinguishing each one in a column.

Study Code: CLOBOF3-16IA01 Date: 09-JUL-2021 NCT No.: NCT04246801

In the listings will show whether the concomitant medication is rescue medication or prohibited medication.

Sponsor: Laboratorios Salvat, S.A.

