6.3.10 Adverse Events

AEs data are collected on the 'Adverse Events' eCRF form.

AEs will be coded according to the Medical Dictionary for Regulatory Activities (MedDRA) system, the latest version and tabulated by System Organ Class (SOC) and by Preferred Term (PT).

A Treatment-Emergent Adverse Event (TEAE) is defined as an AE observed after starting administration of IMP or placebo (see Section 6.3.1).

TEAEs will be summarized by presenting, for each treatment regimen, the number of events and the number and percentage of patients with:

Study Code: CLOBOF3-16IA01 Date: 09-JUL-2021 NCT No.: NCT04246801

Sponsor: Laboratorios Salvat, S.A.

- Any TEAE
- Any Serious Treatment Emergent Adverse Event (STEAE)
- Any TEAE of Special Interest (TEAESI)
- Any TEAE related to IMP/Placebo
- Any TEAE leading to treatment discontinuation (drug withdrawn)
- Any STEAE related to IMP/Placebo
- Any TEAESI related to IMP/Placebo

The number and percentage of TEAEs by causality and the number and percentage of mild moderate and severe TEAEs will be tabulated by SOC, PT and treatment arm. All tables with TEAEs by SOC and PT stratified by treatment regimen will only be counted by patient once within each PT.

The following tables will be provided with TEAEs by SOC and PT stratified by treatment regimen: TEAEs, TEAEs related to IMP/Placebo, TEAEs leading to discontinuation, STEAEs, STEAEs related to IMP/Placebo, TEAESI and TEAESIs related to IMP/Placebo.

TEAEs, STEAEs and TEAESIs will be tabulated by severity (mild, moderate or severe) and relationship to treatment (No: not related, unlikely related, Yes: possible, probable and certain). If a patient has more than one event with the same PT, the AE will only be counted once and the worst/maximal severity and the worst/strongest relationship will be used.

A listing of all AEs will be presented, whether treatment emergent or not. TEAEs will be flagged in this listing. A separate listing for deaths, STEAEs, AESIs and TEAEs leading to discontinuation will be provided (if any).

The following AEs (SOC, PT) of special interest (AESI) will be evaluated by Investigators at all study visits and time points (as applicable):

- IOP rise over 30 mmHg (SOC- INVESTIGATIONS, PT-INTRAOCULAR PRESSURE INCREASED)
- Pain/discomfort associated with IMP instillation (SOC-EYE DISORDERS, PT-EYE PAIN, OCULAR DISCOMFORT and related with IMP)

Additionally, a descriptive table (14.3.1.2.2) of ocular adverse events will be presented by SOC and PT.

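### Measured IOP is tabulated by arm only as by-visit summaries, so no table counts study eyes by worst post-baseline IOP or largest rise from baseline

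*SAP*

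**What the plan says.** **Measured IOP.** SAP 3.3 defines the endpoint as change from baseline at Days 3, 8, 15 and 29. The one table of it, Table 14.3.4.2 (safety set), reads "Summary statistics. Change from Baseline to Day 3, Day 8, Day 15 and Day 29 compared to placebo in intraocular pressure (IOP". SAP 6.3.2 defines summary statistics as n, mean, SD, minimum, quartiles, median and maximum, with a 95% CI of the mean for safety data. Section 5 restricts tables to the study eye. Individual readings are in Listing 16.2.11 (SAP 8.2), "IOP measurementsby Goldman Tonometer".

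**Reported events.** Protocol 8.3.9 makes an IOP rise over 30 mmHg an AE of special interest (AESI), reportable within 24 hours. SAP 6.3.10 maps it to the preferred term for increased intraocular pressure, and Table 14.3.1.9 tabulates it. Table 14.3.1.2.1 is "Treatment Emergent Adverse Events by System Organ Class and Preferred Term", under the rule "All tables with TEAEs by SOC and PT stratified by treatment regimen will only be counted by patient once within each PT". No pressure threshold applies there.

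**The treatment-emergent window.** SAP 6.3.1 gives the date rule "First dose IMP/Pacebo date ≤ start date AE ≤ last dose IMP/Placebo date". SAP 6.3.10 describes a treatment-emergent AE (TEAE) as one seen after dosing starts, states no end date, and refers back to 6.3.1. SAP 3.3 sets AEs up to Day 29 as an endpoint. Protocol 9.1.13 plans by-arm tables of all AEs, but SAP 6.1 says the SAP supersedes the protocol's methods, and its table list has TEAE tables only.

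**Drugs.** A drug is concomitant under "Start date after or on same day as first day of IMP". Table 14.3.10.2 is "Summary of All Concomitant Medications (rescue and prohibited medications included", and Table 14.3.10.3 shows rescue and prohibited drugs.

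**The concern.** Protocol 2.3 lists IOP elevation as a rare effect of ocular corticosteroids, and protocol 8.3.10 calls a rise an expected reaction that could be severe. If only a few eyes respond, the useful summary is how many eyes reached a given pressure or rose by a given amount. A mean dilutes those eyes among the rest, and a maximum shows one eye per visit.

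If the tables hold no such count, a reader must build it by hand from a listing, or rely on what investigators chose to report. Protocol 2.1.4 says no earlier clinical trial of this product exists in the proposed indications, and protocol 2.2 says this one supports a US application. The by-arm picture of a named risk is therefore worth having in a table.

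**Working it through.** The plan states no IOP rate, SD or sample-size figure for IOP, so there is none to reproduce. The check has two parts.

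**1. What the planned outputs count by arm**

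| Kind of rise | By-arm output |
|---|---|
| On treatment, above 30 mmHg | AESI, Table 14.3.1.9 |
| On treatment, 30 mmHg or less, reported as an AE | Table 14.3.1.2.1 |
| Treated with pressure-lowering drops | Drug use in 14.3.10.2 and 14.3.10.3, not a pressure |
| 30 mmHg or less, not reported as an AE | None as an IOP event |
| Starting after the last dose | None under SAP 6.3.1; counted if reported, under the open wording of 6.3.10 |

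On timing, SAP 6.3.8 has "Planned doses=56", and 56 / 4 per day = 14 days, so dosing ends about Day 14, or Day 15 if Day 1 is partial. Visit 5 is Day 29 ± 2, so a rise first seen there starts after the window in 6.3.1. Visit 4 (Day 15 ± 2) can also fall after the last dose.

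**2. How much by-visit summaries would show (illustration)**

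From the documents: 140 active and 70 placebo patients (SAP 4.2) and four post-baseline visits. Assumed: each affected eye has one 10 mmHg rise at a random visit, and the change from baseline otherwise has SD 3 mmHg. Active rates f1 are 1%, 2%, 5% and 8%; placebo rates f0 are 0.25%, 0.5%, 1% and 2%. The low end respects the word rare in protocol 2.3 and the exclusion of previous steroid-related IOP increase.

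An affected eye is shown if it supplies the maximum at any visit. From 20,000 simulated trials per rate, n = 140:

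| f1 | Affected | Shown by maxima | Hidden | P(at least 1 hidden) |
|---|---|---|---|---|
| 1% | 1.4 | 0.9 | 0.5 | about 0.38 |
| 2% | 2.8 | 1.6 | 1.2 | about 0.68 |
| 5% | 7.0 | 2.9 | 4.1 | 0.98 |
| 8% | 11.2 | 3.5 | 7.7 | over 0.99 |

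Mean difference = (f1 − f0) × 10, and half-width = 1.96 × sqrt[(9 + 100·f1(1 − f1))/140 + (9 + 100·f0(1 − f0))/70].

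- All rises at one visit: 0.08 ± 0.88, 0.15 ± 0.91, 0.40 ± 0.96 and 0.60 ± 1.02 mmHg.
- Spread over four visits (f1 and f0 divided by 4): 0.02 ± 0.87, 0.04 ± 0.87, 0.10 ± 0.89 and 0.15 ± 0.91 mmHg.

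Illustrative counts, with exact intervals per arm and Newcombe intervals for the difference:

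- 3/140 = 2.1% (0.4 to 6.1) against 0/70 (upper limit 5.1%): difference 2.1 points (−3.2 to 6.1).
- 11/140 = 7.9% (4.0 to 13.6) against 1/70 = 1.4% (0.04 to 7.7): difference 6.4 points (−0.7 to 12.2).

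**Which cut-off.** Add an assumed baseline mean of 14 to 17 mmHg, SD 3, truncated below 24 mmHg because exclusion 20 bars 24 or more at Visit 1. Then about 3% to 13% of unaffected eyes reach 24 mmHg at some visit by noise alone, roughly 4 to 19 of 140. An observed rise of 10 mmHg or more occurs by noise in 1 − Φ(10/3)^4 = 0.17% of unaffected eyes, or 0.0017 × 140 = 0.24 eyes. The price is sensitivity: an eye whose true rise is exactly 10 mmHg shows 10 or more about half the time, by symmetry, while about 50% to 76% of such eyes would reach 24 mmHg.

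**The case against.** The plan delivers its stated endpoint: change by visit is what SAP 3.3 asks for and what the table gives. The rises that matter most, those above 30 mmHg on treatment, carry 24-hour reporting and their own table. Lower rises count once an investigator reports them as AEs. Pressure-lowering drops are topical ocular drugs prohibited by protocol 6.7.1, so SAP 6.3.9 should place them in the narrower Table 14.3.10.3, including drops started after the last dose. Every reading and every AE is listed. All of this stands and limits the point to a residue.

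Three stronger readings are tempting, and the documents support none of them.

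- **High pressures go uncounted by arm.** The AESI tables contradict this for reported on-treatment rises.
- **Every rise after the last dose is left out.** This holds only if the date rule in 6.3.1 governs. The wording in 6.3.10 would count a reported late rise, although its reference back to 6.3.1 favours the narrower window.
- **The data are lost.** Listing 16.2.11 holds the readings.

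It is also fair to object that the rates, rise size and SDs are all assumed, and that bins on absolute pressure alone would mix real rises with noise. That second objection changes the remedy: the main bin should be size of rise.

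**Conclusion.** The gap is real but narrow. No planned table counts study eyes by worst post-baseline IOP or largest rise. Rises at or below 30 mmHg that are not reported as AEs have no by-arm count as IOP events. Neither do rises starting after the last dose if SAP 6.3.1 governs.

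Under the assumptions above, by-visit maxima would leave between 0.5 and 7.7 affected active eyes unseen on average, and the mean difference would sit well inside its interval. Those sizes move with the assumed rates and SD; the absence of the count does not depend on them.

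A reader might infer that a count would establish a difference between arms. It would not: both illustrative difference intervals include zero, and SAP 6.3.10 keeps safety comparisons descriptive. This is a cheap improvement in safety reporting with no bearing on efficacy inference.

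**What to change.** Keep the by-visit summary. Add one descriptive block to Table 14.3.4.2 (safety set, study eye, by arm), over all recorded readings through Day 29 including Early Termination:

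- n (%) by largest rise from baseline, for example 10 mmHg or more;
- n (%) with worst post-baseline IOP above 30 mmHg, the AESI threshold;
- n (%) with worst value 24 to 30 mmHg, as a secondary and noisier bin. Every eligible study eye starts below 24 mmHg, so reaching it is a new crossing.

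Separately, state in SAP 6.3.1 and 6.3.10 which TEAE window applies. A window running to Day 29 would match the AE endpoint in SAP 3.3. The new block does not settle that question for the AE tables.

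The cost is SAP wording and one table block from data already collected. Early Termination adds few readings: at the expected 4% loss, 0.04 × 210 = 8.4, so at most about 8 patients. The downside is that isolated readings count in both arms, and the 24 mmHg bin will include eyes that cross by measurement noise. Each recorded IOP is already the mean of three valid measures (protocol Appendix 3), which limits this but does not remove it.
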